## **4.2 Scientific Rationale for Study Design**

Respiratory failure due to ARDS is the leading cause of mortality in COVID-19 patients, while myocardial injury is a distinctive feature. In nonclinical and clinical studies of ARDS, regulatory T lymphocytes (T-reg) were shown to attenuate excessive inflammation resulting from infection. CDCs, such as CAP-1002, can target several pathological mechanisms of COVID-19 due to their ability in cell culture to increase T-reg proliferation but not that of other potentially pathogenic T-cell populations.

This double-blinded, placebo-controlled study is designed to assess the safety and efficacy of a novel allogeneic cell therapy, CAP-1002, in treating patients diagnosed with COVID-19 and compromised respiratory status in the context of standard of care. Additional blood samples are collected to explore the effect of CAP-1002 on other biochemical markers of infection and inflammation.

## **4.3 Justification for Dose**

The 150M dose selected for this clinical trial was chosen based on the nonclinical pharmacokinetic profile of CAP-1002 and prior clinical experience in studies performed in subjects with DMD and COVID-19.

selected as a dose

Thus, 150M was

[REDACTED]. Notably, the dose [REDACTED] already demonstrated preliminary efficacy via intracoronary administration [REDACTED] and would be expected to be similarly efficacious via IV administration, given what is known about cell biodistribution and engraftment post infusion by either route.

[REDACTED]

[REDACTED] Thus, the [REDACTED] CAP-1002 dose that was preliminarily effective by intracoronary administration [REDACTED] could be expected to be similarly effective by IV administration, and the proposed 150M CAP-1002 dose can be expected to be equally or possibly more efficacious.

[REDACTED]

[REDACTED]. These collective data suggest that IV infusion of CAP-1002 doses of 150M should be reasonably safe in humans. These data also help define the safety assessments planned for the proposed clinical trial.

[REDACTED]

Thus,

150M CDCs was selected as a dose  
[REDACTED]  
[REDACTED].

#### **4.4 End of Study Definition**

The end of the study is defined as completion of the last visit or procedure for the last enrolled participant (as shown in the Schedule of Activities, [Section 1.3](#)) in the trial globally.

A participant is considered to have completed the study if he or she has completed all phases of the study including the last visit or the last scheduled procedure shown in the Schedule of Activities, [Section 1.3](#). In addition, participants will be considered to have ended the study as follows:

- Death on study
- Withdrawal of informed consent or early termination; all data collected prior to this will remain in the database (refer to [Section 7.2](#)).

### **5 STUDY POPULATION**

#### **5.1 Inclusion Criteria**

Inclusion criteria will be assessed during Screening:

1. Male or female subjects at least 18 years of age at time of consent.
2. Diagnosis of SARS-CoV-2 infection confirmed by real-time reverse transcription polymerase chain reaction (RT-PCR) assay. In the absence of the availability of an RT-PCR test, patients who have previously tested positive for COVID-19 (PCR or non-PCR based methods) and/or in the opinion of the Principal Investigator meet the clinical diagnostic criteria for study inclusion will be eligible for participation in this study.
3. Compromised respiratory status as defined by arterial oxygen saturation < 94% (oxygen saturation measured by pulse oximetry) OR cardiomyopathy due to COVID-19 (defined as a new drop in ejection fraction to  $\leq 50\%$  during COVID-19 with no evidence of obstructive coronary artery disease based on medical records review).
4. Elevation of at least 1 inflammatory marker (IL-1, IL-6, IL-10, TNF- $\alpha$ , ferritin, CRP) defined as  $\geq 2\times$  upper limit of laboratory normal reference value.
5. Written informed consent provided by subject or legal representative.

#### **5.2 Exclusion Criteria**

Exclusion criteria will be assessed during Screening:

1. Currently receiving extracorporeal membrane oxygenation (ECMO) or high frequency oscillatory ventilation (HFOV).
2. Patients who have been intubated.
3. Patients with established positive bacterial blood cultures prior to enrollment or suspicion of superimposed bacterial pneumonia.

4. Patients with untreated human immunodeficiency virus (HIV) infection.
5. Creatinine clearance less than 30 mL/minute.
6. Liver function tests  $> 5\times$  normal.
7. Current or history (within the previous 5 years) of systemic autoimmune or connective tissue disease.
8. Known allergy or hypersensitivity to any of the IP constituents such as dimethyl sulfoxide (DMSO) or bovine proteins.
9. Treatment with a cell therapy product within 12 months prior to randomization.
10. Participation in an ongoing protocol studying an experimental drug or device.
11. Pregnant or breastfeeding female subjects, and sexually active female subjects of childbearing potential not willing to use contraceptive methods.

### **5.3 Lifestyle Considerations**

Not applicable.

### **5.4 Screen Failures**

[figure not shown]
Any subject who provides written informed consent and is ultimately not randomized for whatever reason will be classified as a screen failure. All screen failures may be reviewed with the Medical Monitor to determine whether to re-screen for this study.

### **5.5 Strategies for Recruitment and Retention**

Not applicable.

## **6 STUDY INTERVENTION**

### **6.1 Study Intervention(s) Administration**

### **6.1.2 Dosing and Administration**

The image consists of a series of horizontal black bars of varying lengths, arranged in a staggered, non-linear fashion. The bars are set against a white background. The lengths of the bars decrease from left to right. There are white gaps between the bars, and the overall pattern is irregular and abstract.

The image consists of a series of thick, black horizontal bars of varying lengths and positions. The bars are set against a white background. The overall effect is like a high-contrast photocopy of a document with redacted text. The bars are not perfectly aligned and have some irregular edges, suggesting a low-quality scan or a specific experimental visualization.

### 6.1.3 Post-Infusion Monitoring

Subjects will be monitored for at least 2 hours post-infusion for observation and longer should that be warranted in the judgement of the treating clinician. Investigative sites should observe their local institutional policies for post-parenteral infusion monitoring. In addition to post-infusion observation, an ECG will be conducted within 1 hour post-infusion and vital signs will be monitored every 15 minutes through the 2-hour post-infusion point. A site Investigator will assess the subject for AEs.

#### **6.1.4 Safety Review**

To further reduce the risk, the Medical Monitor will perform a review of cumulative safety data up to Day 7 for the first 6 subjects receiving their dose of IP. During this staged safety review for each of these 6 subjects, no dosing administrations of new subjects will occur. Only after the safety review is completed for each subject and no major safety issues were observed, dosing administration of the next subject will be authorized by the Medical Monitor. Detailed information for this staged safety review is provided in the Medical Monitoring Plan for this trial.

### **6.2 Preparation/Handling/Storage/Accountability**

#### **6.2.1 Acquisition and Accountability**

Good Clinical Practice (GCP) and FDA regulations assign responsibility for IP accountability at the trial site with the Principal Investigator. The Investigator may elect to delegate this responsibility to the investigational pharmacist who is under the supervision of the Investigator.

The site must maintain a record of IP received, prepared, administered, and returned/destroyed. Therefore, IP accountability must always be maintained throughout the trial to show clear product traceability. Details regarding IP accountability will include dates, quantities, batch/serial numbers, expiration dates if applicable, storage conditions, and the unique code numbers assigned to the IP and subjects. IP accountability must adequately document that the subjects were provided the correct treatment assignment and reconcile all IP received from Capricor's drug depot.

Detailed information on IP accountability for this trial are found in the Investigational Product Manual.

All IP materials will be disposed following each IP administration. Site personnel will follow institutional policies on the proper disposal of containers and disposables coming into contact with the IP. Generally, disposal like other biohazard red-bag trash that is ultimately incinerated should be sufficient to meet local institutional policies and any other regulations or laws.

NOTE: SOME STATES REQUIRE THAT THE INVESTIGATIONAL PHARMACY RECEIVING AND PREPARING INVESTIGATIONAL PRODUCT HAVE A VALID TISSUE BANK LICENSE ISSUED BY THE DEPARTMENT OF HEALTH FOR THAT STATE. THE INVESTIGATIVE SITE IS RESPONSIBLE FOR DETERMINING WHETHER A LICENSE IS REQUIRED AND FOR OBTAINING ONE IF REQUIRED AND KEEPING IT CURRENT FOR THE DURATION OF THE ACTIVE DOSING PHASE OF THE TRIAL.

[REDACTED]

[REDACTED]

[REDACTED]

[REDACTED]

A high-contrast, black and white image showing a dark, textured surface with several bright, horizontal bands. The bands are irregular in length and position. In the lower-left area, there is a small, bright, L-shaped mark. In the lower-right area, there is a bright, double-barred L-shaped mark. The overall appearance is abstract and geometric.

the first time in the history of the world, the people of the United States have been called upon to determine whether they will submit to the law of force, or the law of the Constitution. We have said to the world, we will not submit.

The image consists of several black rectangular bars of varying sizes. A large black rectangle is at the top, a white rectangle is in the middle, and a large black rectangle is at the bottom. A small white L-shaped mark is located on the left side of the middle rectangle. The background is white.

The image consists of a series of horizontal bars of varying lengths, rendered in black on a white background. The bars are arranged in a grid-like pattern. Small black shapes, including dots and dashes, are positioned at regular intervals along the bars. The overall effect is similar to a barcode or a technical diagram.

The image consists of a series of horizontal bars of varying lengths and positions, creating a layered effect. The bars are mostly black with some white spaces, suggesting a digital or abstract representation. The bars are arranged in a staggered pattern, with some bars extending beyond the edges of the frame. The lengths of the bars vary, with some being very short and others being quite long. The positions of the bars also vary, with some being near the top and others near the bottom. The overall effect is one of a digital or abstract representation of data or information.

The total dose per treatment is 150M CDCs.

### 6.3 Measures to Minimize Bias: Randomization and Blinding

### 6.3.1 Randomization

Subjects who meet all enrollment criteria will be randomized to receive either CAP-1002 or placebo (1:1 ratio) as outlined in the Manual of Procedures. Only personnel who have been delegated by the Principal Investigator to randomize subjects may complete the task. Subjects will be randomized approximately 1 to 5 days in advance of their first administration. This lead time is to ensure adequate IP shipping time (see IP Manual for shipping specifications). The central randomization will be generated in SAS or comparable software and held in confidence by the statistician preparing the master randomization list.

### 6.3.2 Blinding

This is a double-blind, placebo-controlled trial. Investigational product will be prepared for IV infusion by site personnel who have been appropriately delegated by the Principal Investigator. The IP syringes, once prepared, will appear identical for both treatment groups. However, an investigational pharmacist may be able to differentiate CAP-1002 from placebo on the basis of the opacity of the thawed concentrate observed during IP preparation. For this reason, the investigational pharmacists will have limited interaction with the blinded investigative site personnel.

Site personnel and subjects, staff members at clinical research organizations (CROs), and Capricor personnel will remain blinded to treatment assignment throughout trial conduct. An unblinded DSMB, unblinded statistician, and the DSMB administrator will remain firewalled from any blinded individual involved in trial conduct, services, and/or oversight.

Please refer to [Section 6.3.3](#) for more information related to emergency unblinding of the IP.

### **6.3.3 Emergency Unblinding**

To maintain the overall scientific integrity of the clinical trial, unblinding or code breaks should occur only in exceptional circumstances when knowledge of the actual treatment is absolutely essential for further management and treatment of the subject. Subject safety must always be the first consideration in making such a determination. Investigators are encouraged to discuss this with the Medical Monitor prior to unblinding. In case of an emergency, the Investigator has the sole responsibility for determining if unblinding of a subject's treatment assignment is warranted. If unblinding is deemed to be necessary, the Investigator should use the mechanism for emergency unblinding outlined in the Manual of Procedures. If a subject's treatment assignment is unblinded, Capricor must be notified within 24 hours after breaking the blind. The date and reason that the blind was broken must be recorded in the source documentation. The Investigator is encouraged to maintain the blind as much as possible. Knowledge of the actual allocation can generally be limited and not disclosed to the subject and/or other trial personnel including personnel at other investigative sites, monitors, Capricor, or other personnel involved in the trial; there should be no written or verbal disclosure of the code in any corresponding subject documents. Unblinding should not necessarily be a reason for termination from the trial.

## **6.4 Study Intervention Compliance**

Investigational product will be administered in an inpatient setting per clinical site standards and by appropriately trained medical personnel who will document the actual volume administered at each infusion.

Investigational product administration occurs on study Day 1 after the subject has been deemed eligible and randomized. Should a subject's treatment schedule need to be altered, the Medical Monitor should be contacted to discuss the subject-specific case and out-of-window administration of IP.

## **6.5 Concomitant Therapy**

Use of any concomitant therapies to treat COVID-19 will be documented.

Investigative sites will be requested to provide consistent background standard of care to all enrolled subjects.

## **6.6 Rescue Medicine**

Since all patients with COVID-19 will be managed in an ICU, IV or intramuscular epinephrine and other treatments to manage a severe allergic reaction will be readily available for all patients receiving CAP-1002 in the event of an allergic reaction.

## **7 STUDY INTERVENTION DISCONTINUATION AND PARTICIPANT DISCONTINUATION/WITHDRAWAL**

### **7.1 Discontinuation of Study Intervention**

#### **7.1.1 Early Stopping Rules**

Since a primary concern is not to add risk to subjects who are already considered to be in severe or critical condition from the effects of COVID-19, safety of each enrolled subject will be monitored. Stopping rules on the subject level and study level have been defined to ensure subjects are not exposed to significant risk.

Should a subject-level stopping criterion be met the subject will discontinue the infusion but continue in the trial without receiving any further administration of IP.

Should a study-level stopping event criterion be met enrollment will be halted until a decision to continue, suspend, or terminate enrollment and treatment is made by the DSMB.

The DSMB Charter discusses unblinding of subject treatment assignments to assess stopping rules.

#### **7.1.2 Subject-Level Stopping Rules**

The following stopping rules apply for an individual subject:

- Anaphylactic reaction assessed as related to the administration of IP during the infusion requiring immediate termination of the infusion.
- Hemodynamic compromise, as categorized by new sustained hypotension, assessed as related to the administration of IP during the infusion requiring immediate termination of the infusion.
- Grade 4 AEs during the infusion assessed as related to IP by the clinical care team.

If an individual subject should experience a stopping criterion during the infusion including an anaphylactic reaction, hemodynamic compromise, or Grade 4 AE, as defined by the 3 criteria above, the infusion will be terminated immediately and not restarted.

#### **7.1.3 Study-Level Stopping Rules**

Enrollment and treatment in the trial will be paused in the event any of the following criterion is met:

- Death of a subject within 24 hours of IP administration until the death is adjudicated by the CEC as being unlikely related to CAP-1002.
- Death of a subject occurring at any time after 24 hours of IP administration during the study with cause of death being initially assessed by the Investigator as related to IP and confirmed to be related to CAP-1002 by the DSMB.
- Anaphylactic reaction in a subject during administration of IP or within 24 hours after the infusion initially assessed by the Investigator as related to IP and confirmed to be related to CAP-1002 by the DSMB.

- Two Grade 3 or Grade 4 SAEs initially assessed by the Investigator as related to IP or administration procedure and confirmed to be related to CAP-1002 or administration procedure by the DSMB.

During the enrollment and treatment pause, the CEC will review the observed SAE(s) and adjudicate the event(s) as outlined in the CEC Charter. The DSMB will review the results of the CEC adjudication and determine whether enrollment and treatment should be continued, suspended, or terminated if one of the protocol's study-level stopping criteria is met.

Should any of the events outlined above be reported without assessment of the Investigator or the relationship identified by the Investigator is not related to IP, the trial will continue while the event is adjudicated by the CEC. The CEC will provide the results of the event adjudication to the DSMB for their review and study-stopping rule evaluation. No more than 1 additional subject will be treated within a 24-hour interval after the event has been submitted to the CEC for adjudication and until a study continuation decision has been made by the DSMB.

The recommendation of the DSMB will be one of the following in accordance with the DSMB Charter:

- Continue enrollment per protocol or with modifications
- Temporarily suspend enrollment and/or treatment to obtain additional data or resolve an issue
- Terminate trial due to unfavorable safety signal; significant and unfavorable change in the risk/benefit ratio which could harm or be toxic to participants; scientific value of the trial is insufficient.

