## 4 STUDY DESIGN

### 4.1 Overall Design

This is a randomized, double-blind, placebo-controlled study that will enroll subjects with a clinical diagnosis of COVID-19 confirmed by laboratory testing and who are in severe or critical condition as indicated by life-support measures. Prior to protocol procedures, informed consent will be obtained from the subject or a legally authorized representative. Subjects will undergo a screening evaluation to determine eligibility based on the protocol inclusion and exclusion criteria.

Up to 60 subjects will be enrolled and treated in the study. Replacement of non-treated subjects will be allowed with sponsor agreement.

Eligible subjects will be randomized to either the CAP-1002 or placebo group (1:1 ratio) and undergo baseline safety and efficacy assessments approximately 1 to 5 days prior to the administration of investigational product (IP). Treatment administration consists of 1 peripheral IV infusion of IP (█ █ █ for a total of 150M CDCs or matching placebo) administered at the clinical site. Subjects will receive 1 administration of IP on study Day 1. Background standard of care treatment and practices will be maintained for all patients enrolled in the study.

There is no planned dose adjustment. Should an acute toxicity arise during the infusion (e.g., hypersensitivity reaction or pulmonary decompensation), the infusion should be terminated immediately, and the actual total dose administered recorded. Any decision about re-challenging should be made after discussions with the Investigator, Medical Monitor, and other medical experts who may be required to make an informed decision.

A schematic of the protocol design is provided in [Section 1.2](#) and a summary of all activities is provided in [Section 1.3](#).

Subjects will be randomized in a 1:1 allocation to either the CAP-1002 (150M CDCs) or placebo group. See [Section 6.3.1](#) for additional details related to randomization.

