### 8.3.3.2 Causality of Adverse Event

The Investigator will assess the relationship (causality) of an AE to the IP and administration procedure.

Causality will be defined as follows:

- **Probable:** adverse events that, after careful medical evaluation, are considered with a high degree of certainty to be related to the IP or administration procedure. The following characteristics will apply:
  - A reasonable temporal relationship exists between the event and the IP or administration procedure, and
  - The event is a known reaction to the IP or administration procedure, which cannot be explained by an alternative etiology commonly occurring in the population/individual.
- **Possible:** adverse events that, after careful medical evaluation, do not meet the criteria for a probable relationship to the IP or administration procedure, but for which a connection has reasonable certainty. The following characteristics apply:
  - The event occurs after exposure to the IP or administration procedure, and
  - The event is not a known reaction to the IP or administration procedure, but cannot be explained by a commonly occurring alternative etiology, or
  - In the absence of a temporal relationship, the event cannot reasonably be explained by an alternative etiology.
- **Unlikely:** adverse events that, after careful medical evaluation, do not meet the criteria for possible or probable relationship to IP or administration procedure and for which a connection is unlikely. The following characteristics will apply:

- The event does not follow a reasonable temporal sequence from administration of the IP or administration procedure, or
- May be explained by commonly occurring alternative etiology in the population/individual, or
- May have been produced by environmental factors, and there is no apparent pattern of response to the IP or administration procedure.

An AE will be reported as “related” when causality is evaluated by an Investigator as probably or possibly related to the IP and/or the administration procedure. Related AEs indicate a potential cause-and-effect relationship between the IP and/or administration procedure and the occurrence of the AE.

An AE will be reported as “unrelated” when causality is evaluated by an Investigator as unlikely related to the IP and/or administration procedure by the Investigator. Unrelated AEs indicate no relationship between the occurrence of the AE and the IP and/or administration procedure.

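### Protocol 7.1.3 is internally inconsistent for a death within 24 hours of IP that the Investigator has not assessed or calls not related: one rule pauses the trial, another lets it continue with capped dosing

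*Protocol*

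**What the plan says.** Protocol 7.1.3 lists four criteria under the sentence "Enrollment and treatment in the trial will be paused in the event any of the following criterion is met". The first is "Death of a subject within 24 hours of IP administration until the death is adjudicated by the CEC as being unlikely related to CAP-1002". It sets no condition on the Investigator's view of causality. The other three (a later death, an anaphylactic reaction, two Grade 3 or 4 SAEs) each require that the Investigator has called the event related and that the DSMB has confirmed this.

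The second paragraph after the list opens with "Should any of the events outlined above be reported without assessment of the Investigator" and adds the case where "the relationship identified by the Investigator is not related to IP, the trial will continue while the event is adjudicated by the CEC". Dosing in the meantime is limited: "No more than 1 additional subject will be treated within a 24-hour interval after the event has been submitted to the CEC for adjudication". That limit stays in force until the DSMB has decided on continuation.

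Two other sections bear on the point. Section 7.1.1 halts enrollment once a study-level criterion is met, until the DSMB decides. Section 6.1.4 stops dosing of new subjects while the Medical Monitor reviews data up to Day 7 for each of the first 6 treated subjects. SAP Sections 2 and 7.1 refer back to Protocol 7.1 for the stopping rules and add nothing to them.

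**The concern.** A death within a day of a cell infusion is the event for which a site most needs an unambiguous instruction. As written, whether the next subject is infused before independent adjudication depends on which sentence of 7.1.3 the site or sponsor follows.

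The definitions in 8.3.3.2 make the not-related branch readily available for such a death. One feature of an unlikely relationship is that the event "May be explained by commonly occurring alternative etiology in the population/individual". An event is reported as unrelated "when causality is evaluated by an Investigator as unlikely related to the IP and/or administration procedure". The trial enrolls subjects "who are in severe or critical condition as indicated by life-support measures" (Protocol 4.1), so COVID-19 itself can be offered as the alternative explanation. If the later paragraph governs, the Investigator's judgement (or its absence) decides whether the trial pauses. Bullet 1 appears to reserve that question for the CEC.

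The choice is also a practical one. The trial is multi-center, and subjects are randomized about 1 to 5 days before infusion so that product can be shipped. When a death occurs, other subjects may already be randomized with product on order.

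**Working it through.** No formula applies, and the plan gives no figure to reproduce. The check is to apply each instruction to one case: a subject dies within 24 hours of IP, the Investigator has given no assessment or has called the death not related, and CEC adjudication is pending.

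| Question | 7.1.3, bullet 1 | 7.1.3, later paragraph |
|---|---|---|
| Does it cover this death? | Yes: any death within 24 hours, with no causality condition | Yes: any listed event that is unassessed or called not related; bullet 1 is not excepted |
| What happens during adjudication? | Enrollment and treatment are paused | The trial continues |
| Further subjects dosed meanwhile | 0 | At most 1 in a 24-hour interval |
| Until when? | CEC adjudicates the death as unlikely related | DSMB decides on continuation |

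1. **Same event, same period.** Both rules apply on their words to the same death while the CEC is deliberating. A pause and a continuation cannot both be followed.

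2. **Does one rule override the other?** Bullet 1 is the more specific on timing, and the later paragraph is the more specific on the Investigator's assessment. The section gives no order of precedence. Section 7.1.1 supports a halt, because a death within 24 hours meets bullet 1 by itself, but it does not mention the later paragraph either.

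3. **Does another section decide whether dosing stops?** The staged review in 6.1.4 does so for the first 6 treated subjects, of up to 60. After that stage it gives no hold. Ongoing Medical Monitor oversight (4.1), SAE reporting within 24 hours, and review of all SAEs by the Medical Monitor and CEC (8.3.6) ensure that the death is examined. They do not say whether the next infusion waits.

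4. **What ends the bullet 1 pause?** Bullet 1 ends it at CEC adjudication. Section 7.1.1 and the paragraph of 7.1.3 directly after the list leave the decision to the DSMB. Section 10.1.6.1 treats CEC adjudication as information that guides the DSMB. These can be read as successive steps, but the text does not set out the sequence.

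**The case against.** The best reply is that the section has a natural harmonised reading. Bullet 1 is the only criterion without an Investigator assessment, and it carries its own release condition. Bullets 2 to 4 depend on the Investigator calling the event related, so the later paragraph supplies what they leave open: what to do when that call is missing or negative. Applied to bullet 1, the paragraph would leave its lack of a causality condition with almost nothing to do. Section 7.1.1 points the same way. I think this is probably what was intended. But the paragraph is worded to reach every listed event, so the intention has to be supplied by the reader.

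A second reply is that 10.1.6.2 places further detail in the Safety Monitoring Plan, the DSMB Charter and the CEC Charter, none of which is available here. They may well settle practice. They would not remove the inconsistency from the Protocol, which is the document sites hold and follow.

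A third reply is that continuation is capped and that several safeguards sit behind it. This is correct, and it limits the consequence. A cap is still not a pause.

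**Conclusion.** The inconsistency is real and should be corrected. In the affected case the two instructions differ by 0 further subjects dosed against at most 1 in a 24-hour interval, pending the committees' decisions. For dosing, the difference matters after the staged review of the first 6 treated subjects, while subjects remain to be dosed. The conclusion rests on the Protocol's wording alone; the charters and the Safety Monitoring Plan have not been seen.

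A reader might infer more than this, and three such readings are not supported:

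- **That dosing would go on freely, or that an early death would escape review.** The later paragraph caps dosing, and all SAEs go to the Medical Monitor and CEC.
- **That the affected case is likely.** The documents give no early-death rate. Section 8.3.3.2 bears on how a death would be classified, not on how often one occurs. Although 4.1 speaks of life support, 5.2 excludes intubated patients and those on ECMO or HFOV.
- **That the share of subjects treated after the sixth measures the risk.** It counts enrollment positions only. With no death rate and no CEC or DSMB turnaround time in the documents, the number of subjects who would be dosed under the wrong rule cannot be projected.

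**What to change.** Amend 7.1.3 in two places. Limit the paragraph that lets the trial continue to bullets 2 to 4, and add to bullet 1 the words *whatever the Investigator's assessment*, so that any death within 24 hours of IP pauses enrollment and treatment.

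In the same edit, state in 7.1.1 and bullet 1 whether that pause ends when the CEC adjudicates the death as unlikely related or when the DSMB decides. Check the new wording against the CEC Charter, the DSMB Charter and the Safety Monitoring Plan.

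The cost is a short wording amendment and, in operation, occasional short dosing pauses with rescheduled product. Some of these will be for deaths on placebo or deaths from COVID-19 itself, which bullet 1 already accepts by having no causality condition. No endpoint, sample size or analysis changes.
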